9.2 Secondary Variables and Exploratory Analyses

To investigate diagnostic performance in the subgroup of patients with small lesions (cT1a, dimension ≤ 4 cm in longest diameter), sensitivity and specificity with corresponding Wilson (score) 95% CIs will be calculated for such patients.

In addition to the primary efficacy parameters (sensitivity, specificity), the positive predictive value, the negative predictive value and the accuracy will also be calculated as secondary efficacy parameters using data from patients in the subgroup of tumours ≤ 4 cm in largest diameter. Sensitivity and specificity in the cT1a group will be the key secondary endpoints; while positive predictive value, the negative predictive value and the accuracy in the cT1a group will be additional secondary endpoints.

9.2.1 Predictive Values and Accuracy

a) Positive predictive value (PPV)

The positive predictive value is defined as the probability that a positive histopathology diagnosis was obtained given that the result of the ⁸⁹Zr-TLX PET/CT scan is positive (detection of ccRCC).

$$\text{PPV (\%)} = [\text{TP} / (\text{TP} + \text{FP})] \times 100$$

b) Negative predictive value (NPV)

The negative predictive value is defined as the probability that a negative histopathology diagnosis was obtained given that the result of the ⁸⁹Zr-TLX250 PET/CT scan is negative (no detection of ccRCC).

$$\text{NPV(\%)} = [\text{TN} / (\text{TN} + \text{FN})] \times 100$$

c) Accuracy

The accuracy or probability of a correct test result is defined as the probability that the ⁸⁹Zr-TLX250 PET/CT scan result is correct, i.e., the probability that the PET/CT scan is positive if the histopathological diagnosis for ccRCC is positive or that the PET/CT scan is negative if the histopathological diagnosis for ccRCC is negative.

$$\text{Accuracy (\%)} = [\text{TP} + \text{TN} / (\text{TP} + \text{FP} + \text{TN} + \text{FN})] \times 100$$

9.2.2 Standardised Uptake Value (SUV)

⁸⁹Zr-TLX250 SUVs will be determined for each tumour lesion. Receiver operating characteristics (ROC) will be analysed, to identify a SUV cut-off value, most appropriate to discriminate between ccRCC or non-ccRCC as evidenced by central histology results.

$$\text{SUV} = C_{\text{image}} / (\text{injected dose} / \text{body weight})$$

9.2.3 Inter-reader Variability

Fleiss' kappa statistics will be used to determine the agreement between the qualitative visual assessment of ⁸⁹Zr-TLX250 tumour targeting (tracer uptake in target lesion: yes/no), as assessed by three independent blinded readers. An intra-class kappa of 0.70 or higher will be considered as an acceptable value. Note that both sensitivity and specificity will be determined for each of three independent readers. The study will be successful if the lower bounds of the 95% confidence intervals (CIs) for sensitivity (>70%) and specificity (>68%) in at least the same 2 out of 3 independent readers

9.2.4 Intra-reader Variability

Intra-reader variability will be assessed by having each of the 3 independent blinded readers perform 2 image evaluations on a randomly selected set of 10% cases. A washout period will be introduced between the two interpretations to minimise recall bias. The percent of agreement between the two interpretations will be computed for each reader. Cohen's kappa statistics will be used to determine the reproducibility of the qualitative visual assessment by individual readers when analysing the same data repeatedly.

9.2.5 Sub group analysis

To evaluate sensitivity and specificity of ⁸⁹Zr-TLX250 PET/CT imaging to detect ccRCC in patients with IRMs ≤ 3 cm, IRMs ≤ 2 cm, and Bosniak 3 and 4 lesions.

1. Bosniak 3 and 4 lesions (as determined by the independent central readers)
2. Indeterminate renal masses ≤ 3 cm in largest diameter (as determined by the independent central readers)
3. Indeterminate renal masses ≤ 2 cm in largest diameter (as determined by the independent central readers)

9.2.6 Safety

a) General safety parameters:

Frequency of occurrence and severity of abnormal findings in safety investigations (physical examination, vital signs, 12-lead ECG, clinical laboratory, urinalysis, adverse events, concomitant medication)

b) HACA testing

9.2.7 Exploratory Variables

In situ biological half-life of girentuximab protein in tumour lesions will be estimated, using a general model of average girentuximab kinetics in tumour tissue, derived from serial ⁸⁹Zr-TLX250 imaging. Based on (a) protein residence times in the lesions, (b) an assumed specific activity of therapeutic labelling with Lutetium-177 (¹⁷⁷Lu), and (c) the measured tumour lesion volume (CT dimensions), an achievable therapeutic absorbed dose to tumour (Gy), will be determined for several specific activities and hypothetical activity doses of ¹⁷⁷Lu.

Exploratory analyses will include Extra-renal lesions used as a histology standard of truth (when N1 or M1 disseminated disease is suspected) along with investigations correlating the ⁸⁹Zr-TLX250 tumour lesion SUVs, semi-quantitation of CAIX expression as determined by immunohistochemistry, and evaluation of the distant masses outside the kidney identified on ⁸⁹Zr-TLX250 whole body PET/CT in patients with unexpected evidence of disseminated disease will be conducted.

9.3 Population Characteristics

Population characteristics will include:

- Clinical suspicion of ccRCC due to imaging evidence of indeterminate renal mass of ≤ 7 cm (stage cT1)
- Scheduled for total or partial nephrectomy as part of regular diagnostic work-up at a given date

Summary tables and listings will be provided for demographics and other baseline characteristics, including:

- Age, ethnic origin, sex, physical exam
- Medical/surgical history and baseline findings
- Prior and concomitant medication

10 STATISTICAL METHODOLOGY

10.1 General Considerations

The aim of this study is to evaluate sensitivity, specificity, PPV, NPV, as well as accuracy of ⁸⁹Zr-TLX250 PET/CT imaging using a 37 MBq (1 mCi) activity dose to detect ccRCC in patients with IRM of stage cT1, and who are scheduled for partial or total nephrectomy.

Histological confirmation from nephrectomy (or biopsies of extrarenal lesions from patients in whom unexpected evidence of disseminated disease is observed) will serve as standard of truth. The qualitative assessment of the 3 independent readers will be the primary imaging result.

All data will be listed and trial summary tables will be provided. Descriptive statistics will be presented.

For continuous variables, descriptive statistics will include the number of patients (N), mean, standard deviation (STD), median, first and third quartiles, minimum (MIN) and maximum (MAX) by analysis group and, if applicable, by activity administration and/or time.

Frequencies and percentages will be displayed for categorical data by analysis group and, if applicable, by dose administration and/or time. Percentages by categories will be based on the number of patients with no missing data. Percentages will be rounded off to one decimal place.

The statistical evaluation will be performed by using the SAS software package (version 9.4, or higher).

10.2 Study Population

10.2.1 Disposition of Patients

The following patient data will be summarised:

- Number and percentage of patients enrolled in each analysis set;
- Number and percentage of patients who completed the study or prematurely discontinued from the investigational period by reasons for discontinuation, to be tabulated for each analysis set.
- Patients who are enrolled, but are then either not administered with study drug, or who do not undergo PET/CT imaging after administration of study drug, in whom PET/CT images can not be analysed due to technical failure, or in whom surgical material can not be assessed for presence or absence of ccRCC, are defined as drop-outs. Drop-out patients will be replaced for the primary analysis and study sample size. Missing data is not expected for efficacy outcomes which involve the standard of truth (i.e., sensitivity, specificity, PPV, NPV, accuracy, inter-reader and intra-reader variability)

10.2.2 Protocol Deviations

Major protocol deviations include, but are not limited to the following:

- Wrong study medication administered (e.g., wrong activity, etc.);
- Deviation from any inclusion criteria having an influence on the efficacy outcomes;
- Missing ⁸⁹Zr-TLX250 PET/CT imaging or histopathological diagnosis;
- Administration of prohibited concomitant medication as described in the study protocol

All major protocol deviations will be provided in a listing.

10.2.3 Demographic and Other Baseline Characteristics

Descriptive statistics for age, gender and race at study entry will be presented. Basic statistics for age will be calculated, tabulated and presented by gender. Frequency tabulations for gender and race will be presented.

10.2.4 Previous and Concomitant Medications

Previous and concomitant medications will be coded with World Health Organization ATC Hierarchy list (WHO-ATC). Concomitant medications are those medications or therapies taken after starting study drug administration during investigational period. Patients taking the same medication multiple times will be counted once within “previous” and once within “concomitant”.

All previous and concomitant medications data will be provided in a listing.

10.2.5 Medical, Surgical and Oncology History

All medical, surgical and oncology history data will be coded using the Medical Dictionary for Regulatory Activities (MedDRA). It will be used to summarise disease terms /surgical events by primary system organ class (SOC) and preferred term (PT) and provided in a listing. More details on MedDRA coding are found in the Data Management Plan (DMP).

10.2.6 PET/CT Scan

All image evaluations performed on PET/CT will be provided in tables and listings per reader.

10.3 Study Drugs

Drug exposure and administration data will be provided in a table and listing.

10.4 Analysis of Safety and Tolerability

10.4.1 Adverse Events

The coding dictionary for this study will be Medical Dictionary for Regulatory Activities (MedDRA). It will be used to summarise AEs by primary system organ class (SOC) and preferred term (PT).

A summary table will be provided for the overview of AEs by grade (severity), and overall. The number and percentage of patients with AEs, as classified by primary SOC and PT, as well as the number and percentage of patients with at least one AE, will be summarised by analysis group and overall. Similar summaries will also be provided for AEs related to study drug, serious AEs, AEs leading to study discontinuation and for expected and unexpected AEs. A drug-related AE is defined as any AE with a possible or related to study treatment as assessed by the investigator or with missing assessment of the causal relationship. AEs will be presented as baseline findings and Treatment emergent AEs.

All AEs will also be displayed in listings including their onset and duration.

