Radiation dosimetry was evaluated in a bridging dosimetry study ZIRDOSE investigating the safety and tolerability of Zr-girentuximab. The whole body effective dose for administration of Zr-girentuximab in this phase 1 study was  $0.487 \pm 0.014$  mSv/MBq using the FDA-approved dose calculation tool OLINDA 1.1 and the ICRP 60 standard (Stabin et al., 2005). The absorbed/effective dose was calculated accordingly and resulted in a total whole body effective dose of  $18.0 \pm 0.5$  mSv for 37 MBq. When a newer software IDAC-Dose 2.1 and the ICRP 103 standard (Andersson et al., 2017) is used, the resulting effective dose will be  $0.551 \pm 0.030$  mSv/MBq or  $20.5 \pm 1.1$  mSv for 37 MBq.

Preliminary safety data in the bridging study (ZIRDOSE) with Zr-girentuximab administered to 5 patients per 5 mg and 10 mg girentuximab mass dose, each, did not prompt any safety concern over the treatment. In the course of the study, no treatment-related SAEs or SUSARs were reported from any of the 10 patients. The severe SAE of postoperative bleeding was considered by the investigator as not related to the study treatment. A total of 7 AEs were experienced by 4 patients. An unlikely or no relationship to treatment was assessed by the investigator for 6 AEs. Mild nausea in one patient was considered by the investigator as possibly related to the study treatment.

All patients within the present phase 3 ZIRCON trial will undergo an abdominal PET/CT scan. The CT scan will be a low-dose CT for the purpose of attenuation correction of the PET data only. In

order to keep the effective dose of this abdominal low-dose CT within a specified limit of 1 mSv, or less, the acquisition parameters for the low-dose CT will be restricted. These parameters for imaging will be defined in a separate subject imaging manual.

The combined whole body effective dose of Zr-girentuximab administration and abdominal low-dose CT is expected to be below 20 mSv based on the accepted standard OLINDA 1.1 and ICRP 60, or below 23 mSv based on IDAC-Dose 2.1 and ICRP 103, for all patients. The lifetime attributable risk for incidence of radiation-induced cancer for an effective dose of 23 mSv is 0.4% (ICRP 103, 2007), which is comparable to the risk from a diagnostic CT of chest, abdomen and pelvis (Smith-Bindman et al., 2009).

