#### ***Causal relationship to study drug***

The possible causal relationship between the AE and the administration of the study drug is classified according to the following question:

*"Is there a reasonable likelihood that the event was caused by the study drug?"*

Possible answers are:

- Related (plausible time relationship to the administration of IMP/RP. No plausible explanation by underlying/concurrent disease or other drugs/events),
- Possible (plausible time relationship to the administration of IMP/RP, but the AE can be also plausibly explained by the underlying/concurrent disease or other medicinal products / events),
- Unlikely (unlikely temporal relationship to the administration of IMP/RP. Other medicinal products, events, and the underlying/concurrent disease provide a plausible explanation)
- Not related (clear evidence that the AE is not connected to the IMP/RP administration)
- Not assessable (no evaluation possible based on present data, additional clarification and follow-up necessary)

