### 9.2.3 Statistical Analyses

Statistical analyses will be performed after database lock, after all study data including the final study visit have been collected and cleaned.

For all variables (primary and secondary), the statistical analyses in this study will be descriptively using exploratory statistics.

Descriptive analyses will include:

- Mean, standard derivation, median and range for continuous variables,
- Median, range and frequency distribution for discrete (ordinal) variables,
- Frequency distribution for nominal variables

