8.2 Safety Analysis Set

The Safety Analysis Set (SAF) will consist of all patients who received ⁸⁹Zr-TLX250.

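### Does SAP 10.4.1 need a rule for adverse events whose causality is rated not assessable?

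*SAP*

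**What the plan says.** Protocol 8.8.2.2 (causal relationship to study drug) offers five answers: related, possible, unlikely, not related and not assessable. The last is worded "Not assessable (no evaluation possible based on present data, additional clarification and follow-up necessary".

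SAP 10.4.1 defines a drug-related event as one "with a possible or related to study treatment as assessed by the investigator or with missing assessment of the causal relationship". The definition feeds one named set of tables: "Similar summaries will also be provided for AEs related to study drug, serious AEs, AEs leading to study discontinuation". These follow the pattern of the main AE table, which reports "The number and percentage of patients with AEs, as classified by primary SOC and PT", so the unit counted is the patient. On the population, SAP 8.2 states: "The Safety Analysis Set (SAF) will consist of all patients who received" the tracer.

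On timing, Protocol 9.2.3 states: "Statistical analyses will be performed after database lock, after all study data including the final study visit have been collected and cleaned".

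**The concern.** The SAP sentence takes a cautious line: where causality is unknown because nobody recorded it, the event counts as drug-related. *Not assessable* is also unknown causality, but it is a completed answer and the sentence does not name it. On a strict reading, an empty field is counted and an explicit statement that no judgement was possible is not, which runs against the sentence's own caution. On a looser reading, both are a missing assessment and both are counted. Two programmers working from the same SAP could therefore report different numbers of patients with drug-related events.

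At stake is the accuracy of the drug-related summary in a trial where safety and tolerability is a secondary objective.

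**Working it through.** There is no stated figure to reproduce, because the question is how a category is classified. The check sets the two texts side by side, looks for any other rule, and then bounds the effect of one patient.

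**1. Mapping the protocol's answers to the SAP definition**

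| Entry in the causality field | Status under SAP 10.4.1 |
|---|---|
| Related | Counted |
| Possible | Counted |
| Left blank | Counted, as a missing assessment |
| Unlikely | Not counted |
| Not related | Not counted |
| Not assessable | Not named: out if read strictly, in if read as a missing assessment |

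**2. Any other rule.** SAP 10.7.1 applies a worst case to AEs, but only for incomplete dates and times. Protocol 8.8.2.4 describes an adverse drug reaction as one whose causal link cannot be excluded. That points towards counting these events, but it is a reporting definition that the SAP does not cite. Neither text closes the gap formally.

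**3. Which reading fits better.** The protocol's own gloss on *not assessable* is that no evaluation could be made on the data at hand. An event that could not be evaluated has, in substance, no causality assessment. Counting it matches the cautious intent of the SAP sentence.

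**4. Which events are left.** The gloss also makes the answer provisional, since it calls for clarification and follow-up. Patients are asked about events at every assessment until the end of study (Protocol 8.8.2.3), eCRF discrepancies are queried (Protocol 10.1.2), and analysis waits for cleaned data. Only events unresolved after all of that are affected. Nothing guarantees that there are none.

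**5. Effect of one patient.** The overall percentage changes only for a patient who has an unresolved *not assessable* event and no other event already counted. Otherwise only SOC or PT rows can change. Shift in percentage points = 100 × 1/N, where N is the size of the safety set.

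- N = 252 (protocol planned size): 100/252 = 0.40
- N = 300 (size in SAP 5.1 and SAP 6): 100/300 = 0.33

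Every evaluable patient has been dosed, and dosed drop-outs also belong to the safety set. If the evaluable target is met, N is at least these values and the shift is at most these amounts.

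**6. How many such patients.** This cannot be derived. Protocol 1.3 reports 7 AEs in the bridging study: "An unlikely or no relationship to treatment was assessed by the investigator for 6 AEs", and one was rated possibly related, so 6 + 1 = 7 and none was left unrated. Those 7 events came from only 4 of the 10 patients, the data are called preliminary, and the text does not say whether that study offered a *not assessable* answer. No rate is taken from it.

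**The case for a change.** The best case for a change is that this table carries more weight here than in a controlled trial. There is no comparator. AE recording runs through nephrectomy and, when surgery falls after Day 28, to 35 ± 7 days beyond it (Protocol 7.5 and 7.7.2). Protocol 1.3 puts the overall complication rate of that surgery at up to 20%. The all-AE table may therefore hold many surgical events, and investigator causality is the main planned way to separate them from events due to the tracer. A definition used for that purpose should have one reading, fixed before the counts are known, and one clause would achieve it. It is also not certain that only one table is touched: SAP 10.4.1 plans summaries of expected and unexpected AEs, and the protocol defines those terms partly through adverse drug reactions.

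Part of this stands. The definition is open to two readings, and the drug-related table does matter in a single-arm study. The documents do not settle whether causality feeds the expected and unexpected summaries.

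It does not follow that the safety conclusion is exposed. Surgical complications are unlikely to be the main source of unresolved causality, since they have an obvious alternative explanation, for which the scale provides other answers. Events that do remain *not assessable* are still in the all-AE summary, in the serious-AE summary if serious, and in the listings. SAP 10.1 commits to listing all data, so either count can be recovered.

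**Conclusion.** This is a gap in detail that analysts fill sensibly, and the plan can stand. The SAP does not name one of the five causality answers, but its rule for missing assessments, read with the protocol's description of that answer, leads to a natural choice: count events still *not assessable* at database lock as drug-related. Recording that in the table specification is ordinary programming practice and needs no SAP change.

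The effect is at most about 0.3 to 0.4 percentage points in the overall drug-related figure for each affected patient, confined to a descriptive safety summary. The number of such patients is unknown but probably very small after follow-up and data cleaning. That expectation is a judgement; the documents give no figure for it.

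The co-primary and key secondary analyses do not use AE causality. The IDMC's remit under SAP 7.1 is limited to accrual and histology counts, so no monitoring decision rests on it. The safety conclusion would be sound under either reading.

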10.4.2 Laboratory results

Haematology, Biochemistry, Clotting parameters, Urinalysis and Immunogenicity data will be provided in a listing and summarised in tables. Clinical significance will be presented as a flag on the laboratory listings. Change from baseline will be calculated and statistical significance will be tested using Wilcoxon signed-rank test. Figures to show laboratory results trend over time will be provided.

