
Plan for statistical analysis
	
To take multiple testing for the two co-primary endpoints into account, testing will occur in a strictly sequential order. Firstly, the observed sensitivity will be compared against a predefined minimum expected threshold for sensitivity, using a binominal confidence interval. If the null hypothesis for sensitivity testing can be rejected, the test for specificity is performed using the same methodology, applying a predefined threshold for specificity. This strategy ensures a global level of significance of <math>p < 0.05</math>.
 
Reader variability, as the most important secondary objectives will be determined using Kappa statistics.
 
All other secondary variables will be analysed descriptively using exploratory statistics.

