### **8.8.2.5 Serious Adverse Events**

#### ***Definition of Serious Adverse Events***

The following SAE definition is based on ICH guidelines and the final rule issued by the Food and Drug Administration (FDA) and effective 06 Apr 1998. It is to be applied to both, AEs (defined in Section 8.8.2.1) and baseline findings (defined in Section 8.8.1).

An SAE is classified as any untoward medical occurrence that at any dose

- Results in death, or
- Is life threatening, or
- Requires inpatient hospitalization or prolongation of existing hospitalization, or
- Results in persistent or significant disability / incapacity, or
- Is a congenital anomaly / birth defect.

The term 'life threatening' in the definition refers to an event in which the patient was at risk of death at the time of the event, it does not refer to an event which hypothetically might have caused death if it were more severe.

Medical and scientific judgment should be exercised in deciding whether it is appropriate to also report an AE as serious in other situations, such as important medical events that may not be immediately life threatening or result in death or hospitalization but may jeopardize the patient or may require intervention to prevent one of the other outcomes listed in the definition above. These should also usually be considered serious. Examples of such events are intensive treatment in an

emergency room or at home for allergic bronchospasm; blood dyscrasias or convulsions that do not result in inpatient hospitalization; or development of drug dependency or drug abuse.

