10.4.3 ECG results

ECG results data will be provided in a listing and summarized in a table by time point. Clinical significance will be presented as a flag on the ECG listings and summary table will be provided.

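### The laboratory significance tests are not limited to samples taken before nephrectomy, and the adverse-event tables have no split at surgery

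*SAP*

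**What the plan says.** SAP 10.4.2 plans listings, summary tables and trend figures for the laboratory data, and adds a test: "Change from baseline will be calculated and statistical significance will be tested using Wilcoxon signed-rank test". It does not say which post-dose visit is tested, or whether baseline is the screening sample or the Day 0 pre-dose sample. SAP 10.1 provides summaries of continuous variables "by analysis group and, if applicable, by activity administration and/or time", with no cut at surgery. For ECGs, SAP 10.4.3 plans no test: "ECG results data will be provided in a listing and summarized in a table by time point".

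The protocol describes a descriptive analysis. Section 9.2.3 states: "For all variables (primary and secondary), the statistical analyses in this study will be descriptively using exploratory statistics". The Synopsis, after the co-primary endpoints and reader variability, states: "All other secondary variables will be analysed descriptively using exploratory statistics".

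For adverse events, SAP 10.4.1 plans tables of all events, drug-related events, serious events, events leading to discontinuation, and expected and unexpected events. The only division in time is between baseline findings and treatment-emergent events, which is a cut at dosing. Onset appears in listings only. Protocol 7.1 has events recorded continuously from Day 0 to end of study, so collection runs through the nephrectomy.

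**The concern.** Every eligible patient receives the tracer, and nearly all then have part or all of a kidney removed. A change from baseline measured after the operation contains the effect of the tracer, the effect of surgery and the effect of recovery. A signed-rank test on that change asks only whether it is centred on zero. It cannot say why it is not, and no untreated group is available for comparison. The tested panel includes haemoglobin, creatinine and urea.

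The adverse-event tables have the same difficulty. One criterion for a serious event is: "Requires inpatient hospitalization or prolongation of existing hospitalization". A complication that lengthens the surgical stay is therefore serious by definition, and it is counted in the same table as an event between dosing and surgery. A reader of the study report could take a final-visit p-value or a serious-event count as evidence about the tracer when it reflects the operation.

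**Working it through.** The documents give no figure for the laboratory tests, so there is none to reproduce. The check rests on the visit windows and on the protocol's own rates.

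**1. Is the final-visit sample postoperative?** Inputs are Protocol 7.4, 7.5, 7.7.1, 7.7.2 and 8.8.3.
- Surgery by Day 28: the final visit is Day 42 ± 7, so Day 35 to 49. The shortest gap is 35 − 28 = 7 days. Imaging is not before 72 hours, so the earliest possible surgery is Day 3 and the longest gap is 49 − 3 = 46 days.
- Surgery after Day 28: the final visit is 35 ± 7 days after surgery, so 28 to 42 days.

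No scheduled final-visit sample precedes a per-protocol nephrectomy. The exceptions are patients who withdraw early and complete final-visit procedures then (Protocol 4.3.3), and patients whose nephrectomy is cancelled or replaced by a biopsy (Protocol 3.1, 7.5).

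**2. What share of post-dose draws is postoperative?**
- Protocol 8.8.3 lists Day 5 and the final visit: 1 of 2.
- Protocol Table 4, surgery by Day 28, lists Day 5, pre-surgery, and Day 42 as the final visit: 1 of 3.
- Protocol Table 4, later surgery, lists Day 5, Day 42, pre-surgery and the final visit: 1 of 4, or 2 of 4 if Day 42 falls after surgery. If later surgery is assumed uniform over Days 29 to 90 (62 days), then 13/62 = 21% are already operated on before Day 42 (6/62 = 10% if the visit is on Day 35, 20/62 = 32% if on Day 49).
- Volume check on Table 4: 23 + 20 + 4 × 18 = 115 mL, and 115 − 18 = 97 mL. Both agree with Protocol 8.9.

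**3. Would the test react to surgery alone?** The documents give no size for surgical laboratory shifts, so a range was assumed. The simulation used 2,000 runs, normally distributed changes, full attendance, a two-sided 5% level and no tracer effect. The shift is in SDs of the change.

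| Shift due to surgery | Rejection, N = 252 | Rejection, N = 300 |
|---|---|---|
| 0 | 4.8% | 4.5% |
| 0.1 SD | 35% | 39% |
| 0.2 SD | 88% | 92% |
| 0.3 SD | 99.7% | 100% |

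The two sizes are the protocol's 252 and the SAP's 300. With pre-surgery samples only, the surgical shift cannot enter and the zero row applies.

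**4. How much of the adverse-event window follows surgery?** The share is (end day − surgery day) / end day at nominal visit days:
- surgery on Day 6: 36/42 = 86%
- Day 28: 14/42 = 33%
- Day 29: 35/64 = 55%
- Day 60: 35/95 = 37%
- Day 90: 35/125 = 28%

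**5. How many surgical events might enter the tables?** Protocol 1.3 cites up to 20% overall complications after nephrectomy: 0.20 × 252 = 50.4 and 0.20 × 300 = 60. This is an illustration and not an upper bound, because adverse events are defined more broadly than complications and the safety set is all dosed patients.

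**6. Do such events reach the serious-event data?** In the bridging study they did: "The severe SAE of postoperative bleeding was considered by the investigator as not related to the study treatment". The same paragraph reports that "no treatment-related SAEs or SUSARs were reported from any of the 10 patients". One in 10 is 10% (Wilson 95% CI 1.8% to 40%), far too imprecise to estimate a rate. It does show the route: the event is absent from the related count and present in the serious count.

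**The case against.** The strongest reply is that the plan already lets a careful reader separate the two causes. The Day 5 sample precedes surgery, and change from baseline with trend figures is most naturally analysed visit by visit. No hypothesis, alpha or decision rule is attached to the laboratory p-values. For adverse events, Protocol 8.8.2.1 does not count the planned operation itself as an event. A drug-related table is planned, with causality options that include unlikely and not related. All-event and serious-event tables are meant to count events regardless of cause.

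Much of this stands. Day 5 is not confounded by surgery, and leakage into the drug-related table is probably small, although SAP 10.4.1 also counts events with missing causality there. But by-time summaries apply only where applicable, and neither they nor the figures restrict the test. Complications still enter the tables, and onset in a listing is not a planned summary.

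Two supporting arguments are weak. ECGs are taken only up to 2 hours after dosing, so SAP 10.4.3 is a model for layout but no precedent for postoperative data. Protocol 9.2.3 is loosely worded, since read literally it would also cover the co-primary endpoints, which 9.2.3.1 tests. The Synopsis sentence is the better support. Calling the analyses exploratory does not strictly forbid a nominal p-value.

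**Conclusion.** The concern holds. Followed as written, SAP 10.4.2 gives final-visit p-values that cannot bear on tracer safety, and SAP 10.4.1 mixes events before and after surgery in the all-event and serious-event tables. The conclusion about the laboratory tests rests on the visit windows and the single-arm design alone. Its practical size is not known from the documents: the rejection rates depend on assumed shifts, and the complication counts depend on a cited maximum rate.

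The consequence is confined to interpreting secondary objective 7. No co-primary endpoint, key secondary endpoint or success rule is affected. The change is worth making because it is cheap and the design offers no other correction.

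**What to change.** 1. **SAP 10.4.2.** Present laboratory change descriptively by visit and delete the signed-rank tests. Alternatively, limit them to post-dose samples taken before surgery, using sample time or a stated rule for day-of-surgery samples, and label them exploratory. In either case, say which sample is baseline.
2. **SAP 10.4.1.** Keep the overall tables. Add a split of the all-event and serious-event tables into dosing to surgery and surgery to final visit. Put all follow-up in the first period for patients without surgery, state a rule for events with onset on the day of surgery, and report follow-up time per period.
3. **Separately, reconcile the laboratory schedule.** Protocol Table 1 footnote H and Table 4 include a pre-surgery draw, and Table 4 also has a Day 42 draw in addition to the final visit. Sections 7.5, 7.6 and 8.8.3 do not list these. The restricted test in item 1 depends on which pre-surgery samples exist.

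The cost is SAP wording, one period flag and person-time in the safety programming. The surgery date is needed anyway to schedule the final visit, and onset is already listed. The documents do not show whether sample time is captured, so this should be confirmed.

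There are limits. Late tracer effects would fall in the post-surgery column. Early-operated patients, expected to be a minor proportion, add little to the first period. Tests limited to pre-surgery samples would still be uncontrolled.
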